### **6.11.2. Gated Secondary Efficacy Analyses**

Bretz's graphical approach may be utilized to provide strong control of the study-wise type I error rate for the primary and key secondary hypotheses at a two-sided alpha level of 0.05 (Bretz et al. 2009, 2011). The DPM analyses will be conducted on the iADRS, CDR-SB, ADAS-Cog13, iADL and MMSE scores, and statistical significance will be determined based on the following multiplicity graph of hypotheses regarding the IV infusion of LY3303560 slowing the cognitive and/or functional decline of AD:

iADRS = DPM analysis of iADRS

CDR-SB = DPM analysis of CDR-SB

iADL = DPM analysis of iADL

ADAS-Cog13 = DPM analysis of ADAS-Cog13

MMSE = DPM analysis of MMSE

The preceding graphical testing scheme is outlined using alpha levels in a frequentist testing paradigm. The primary efficacy analysis for this trial is the Bayesian DPM. The following describes how probability thresholds will be developed for each test (and potential test) in the graph that control the false positive rate at the appropriate corresponding alpha level. The tests for each scale will all be of the form  $\Pr(\text{DPR} < 0.75) > X$ , where the value of X is determined via simulation to control the test at the corresponding alpha level.

To test the hypothesis of a disease progression benefit, the posterior probability of superiority in cognitive/functional slowing will be calculated, and if it is above a pre-specified threshold (which controls the false positive rate at approximately 2.5%), then a statistical significant claim of cognitive/functional slowing will be made. Success will be declared at a graphical node if the posterior probability of at least 25% slowing is greater than a certain threshold, where the threshold is determined via simulation to control the false positive rate under the null scenario for a given scale. The null scenario used in these simulations to determine the posterior probability thresholds will be the overall mean trajectory from the blinded LMDC trial data, conducted at a date late in the trial but prior to unblinding. As a sensitivity analysis of the selected posterior probability thresholds, additional simulations may be run after unblinding using the unblinded data to understand the impact of the choice of variance-covariance matrix and mean placebo trajectory on the posterior probability thresholds used to control the false positive rate.

Assuming the null scenario of 0% slowing in treated arms relative to the placebo, synthetic data are sampled from a multivariate normal distribution for each endpoint that accounts for the correlation between visits after adjusting for concomitant drug use, pooled site, and age. The mean trajectory and variance-covariance matrix for each scale is the overall (i.e. treatment-naïve) least-squares mean (from frequentist MMRM analyses adjusting for pooled site, baseline AChEI/memantine use and age) at each visit in the blinded trial data. The Bayesian DPM is fit to each simulated dataset and the posterior probability of at least 25% slowing is calculated. The threshold is the value at which approximately  $(\alpha/2 \times 100)\%$  of the simulated posterior probabilities are larger. The cutoff for the primary analysis of LY5600 is 0.51 ( $\Pr(\text{DPR} < 0.75) > 0.51$ ); the cutoff for LY1400 is 0.99928 ( $\Pr(\text{DPR} < 0.75) > 0.99928$ ). The other thresholds will be calculated in the same way.

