## 6.5. Multiple Comparisons/Multiplicity

A graphical strategy may be used for testing key secondary hypotheses to protect against Type I error of falsely rejecting a null hypothesis (Section [6.11.2.](#)). The use of a prespecified analysis plan that employs Bretz' graphical approach will provide strong control of the study-wise Type I error rate for the primary and key secondary hypotheses at level  $\alpha=0.05$  (Bretz et al. 2009, 2011).

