For subject level random effect  $\gamma_i \sim N(\mu_\gamma, \sigma_\gamma^2)$ , a diffuse normal prior is assumed for  $\mu_\gamma$ , the mean of the subject level random effect and a diffuse inverse gamma prior is considered for  $\sigma_\gamma^2$ , the variance of the subject level random effect:

$$\mu_\gamma \sim N(0, 10^2), \sigma_\gamma^2 \sim IG(0.005, 0.005).$$

A diffuse normal prior distribution is assumed for each mean change in disease progression from visit  $v - 1$  to visit  $v$  in the placebo,  $\alpha_v$ :

$$\alpha_v \sim N(1.25, 900)$$

A normal prior distribution  $N(0,4)$  is assumed for the  $\log(\text{DPR})$  parameter of each active treatment arm (i.e.,  $\theta_1$  and  $\theta_2$ ). For the error term  $\epsilon_{ij} \sim N(0, \sigma_\epsilon^2)$ , an inverse gamma prior is assumed for the model error variance:

[figure not shown]
$$\sigma_\epsilon^2 \sim IG(0.005, 0.005).$$

Diffuse normal prior of the form  $N(0,100)$  is used for each baseline covariate (pooled site ID, age and baseline AChEI/memantine use (yes/no)) in the model. A DPR less than 1 favors LY3303560 and corresponds to a slowing of disease progression with LY3303560 in comparison to placebo; similarly, a DPR greater than 1 favors placebo. The DPM will be fit to the data and Bayesian inferences will be summarized including posterior distribution of DPR and posterior probabilities of various DPR thresholds of interest (for example, 0.75 which translates to 25% slowing of disease progression with LY3303560 group versus placebo). To test the hypothesis of a disease progression benefit, we calculate the posterior probability of superiority in cognitive/functional slowing and if it is above a pre-specified threshold (which controls the false positive rate at the values in the graphical testing scheme), then a claim of cognitive/functional slowing will be made. The null hypothesis is that the DPR between the LY3303560 group versus placebo equals 1.

In addition, Bayesian posterior probability of active treatment arm being superior to placebo by at least a margin of interest will also be calculated assuming a noninformative prior.

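### Strong type I error control is claimed, but the gate cutoffs are calibrated only with both doses inert; the LY5600 node's true level shifts with the effect of 1400 mg

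*SAP*

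**What the plan says.** SAP 6.11.1 defines the hypothesis: "The null hypothesis is that the DPR between the LY3303560 group versus placebo equals 1". SAP 6.11.2 gives the decision rule: "Success will be declared at a graphical node if the posterior probability of at least 25% slowing is greater than a certain threshold". The rule therefore works at DPR 0.75 while the null sits at DPR 1.

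The cutoffs come from simulation. The mean trajectory "will be the overall mean trajectory from the blinded LMDC trial data", taken late in the trial before unblinding, so it averages over all three arms. The configuration is a single one: "Assuming the null scenario of 0% slowing in treated arms relative to the placebo". SAP 6.11.2 then states two results. "The cutoff for the primary analysis of LY5600 is 0.51", and the LY1400 cutoff is 0.99928.

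The claim attached to this is general. SAP 6.5 says that the graphical plan "will provide strong control of the study-wise Type I error rate for the primary and key secondary hypotheses", and 6.11.2 repeats "strong control of the study-wise type I error rate for the primary and key secondary hypotheses at a two-sided alpha level of 0.05". The only check on the calibration is optional and comes late: "additional simulations may be run after unblinding using the unblinded data to understand the impact of the choice of variance-covariance matrix and mean placebo trajectory". The SAP does not say what follows if that check disagrees with the cutoffs.

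**The concern.** Strong control means that the error rate holds under every combination of true and false nulls. A Bretz graph delivers it only if each node's test keeps its level whatever is true of the other hypotheses.

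Here it need not. When the boundary in the posterior statement (0.75) differs from the null value (1), the distance between them in standard errors is proportional to the placebo decline. A cutoff that gives 2.5% at one decline gives a different level at another. The cutoff is set at the pooled decline, but the test runs against the placebo decline. If the other dose slows decline, the pooled curve is shallower than placebo and the cutoff is too strict. If the other dose speeds decline, the pooled curve is steeper and the cutoff is too lax.

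At stake is whether the report may describe a positive LY5600 node as strongly controlled at the stated level, or only as controlled when neither dose does anything.

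**Working it through.** **Inputs.** From SAP 5.2: 360 patients, 30% dropout, placebo decline 19.56, SD 20.9 at Week 104, slowing of 33% (1400 mg) and 50% (5600 mg), and a criterion of posterior probability at least 0.6 for 25% slowing. From 5.1 and 5.3: 1:1:1 allocation. From 6.11.2: cutoffs 0.51 and 0.99928. Assumed: equal arms, effects proportional to placebo decline, blinded covariance equal to the true one, and the full one-sided 2.5% at the LY5600 node. The last is an assumption because the multiplicity graph is not visible in the text at hand.

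**Formula.** With n effective patients per arm, Pr(DPR<0.75) > X is approximately

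(0.75·m_placebo − m_active)/se > z(X), with se = SD·√((1 + 0.75²)/n).

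If the active dose has DPR 1 and the true placebo decline is D, the level is Φ(−(0.25·D/se + z(X))).

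**Reproducing the design figures.** Section 5.2 gives more than 95% power for at least one arm and about 2.5% false positives with both arms inert. Taking n from 84 (120 × 0.7) to 120, the approximation gives 95.3% to 97.6% power, ignoring the 3-month delay. The false positive rate for either arm runs from 4.6% down to 2.1%, and is 2.5% at about n = 110. The approximation is compatible with the plan's own figures.

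**LY5600 node at X = 0.51.** Here z(0.51) = 0.025. A level of 2.5% at the pooled decline P requires 0.25·P/se = 1.960 − 0.025 = 1.935. If 1400 mg has DPR r and 5600 mg is truly null, P = D·(2 + r)/3, so 0.25·D/se = 1.935·3/(2 + r).

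| DPR of 1400 mg, r | P/D | 1.935·3/(2+r) + 0.025 | True level |
|---|---|---|---|
| 0.50 | 0.833 | 2.347 | 0.95% |
| 0.67 | 0.890 | 2.199 | 1.4% |
| 1.00 | 1.000 | 1.960 | 2.5% |
| 1.30 | 1.100 | 1.784 | 3.7% |
| 1.36 | 1.120 | 1.753 | 4.0% |

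If the node held 2.0% instead, the levels would be 0.7% at r = 0.50 and 3.2% at r = 1.33. Sampling error in the pooled mean adds no inflation: with both doses inert the level is then 2.4%.

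**Longitudinal cross-check.** Simulated 12-weekly data with random intercepts and slopes, 30% dropout and a fitted disease progression model gave 1.3%, 1.3%, 1.9% and 3.9% at r = 0.50, 0.67, 1 and 1.33 (4,000 trials per cell). The gradient is the same; individual values move with noise and assumptions.

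**LY1400 node at X = 0.99928.** Here z = 3.19. The level at the calibration decline is Φ(−(1.935 + 3.19)), about 1.5 × 10⁻⁷, if the posterior is well calibrated. It is about 0.02% to 0.14% if the model standard error is 2 to 3 times too small. The table does not describe this node.

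**Cutoffs re-derived from the observed placebo mean.** Replacing P by m_placebo gives z(X) = 1.96 − 0.25·m_placebo/se. The rule becomes m_placebo − m_active > 1.96·SD·√(1.5625/n), while the true standard error of that difference is SD·√(2/n). With both doses inert the level is Φ(−1.96·√(1.5625/2)) = Φ(−1.732) = 4.2%, whatever the decline, SD or n.

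**The case against.** The best defence has four parts.

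- **Control holds where the sponsor expects to be.** With the planned slowing, or with inert doses, the LY5600 level is at or below 2.5%. This stands. A reader might take the 1% end as an error-control failure, but it is a conservative test that costs some power.
- **Inflation needs a narrow corner.** 1400 mg must be clearly harmful while 5600 mg is exactly null. In the reverse case 5600 mg almost never rejects, and as far as the stated cutoffs show, 1400 mg stays at 0.99928, where its error is far below 2.5%. This also stands. A reader might infer that study-wise error is generally inflated, or that every node runs between 1% and 4%; the documents support neither.
- **The limitation is partly disclosed.** Section 6.11.2 ties the thresholds to the null scenario, and 5.2 gives its false positive rate only for two placebo-like arms. But 6.5 and the opening of 6.11.2 carry no such qualification.
- **The post-unblinding simulations decide nothing.** They are optional and meant for understanding. A reader might infer that the trial's claim would run at 4.2%; the plan does not say that any claim will be re-decided that way. The figure shows only why re-derived cutoffs would be a misleading check.

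Two further limits apply. A power loss on 1400 mg at full level cannot be established without the graph. And the 25% slowing criterion is the sponsor's design choice, so its use is not itself an error.

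**Conclusion.** The claim is wrong as written. Strong control is asserted over all configurations, but the calibration covers one, and it preserves the LY5600 level only when 1400 mg is inert or beneficial. For a full-level LY5600 node the true level is about 1% when 1400 mg halves decline, 2.5% when both doses are inert, and 3.7% to 4.0% when 1400 mg speeds decline by 30% to 36%.

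The direction follows from the form of the rule. The sizes rest on the normal approximation and the assumptions listed with the inputs. Cutoffs for the secondary scales are not stated, so their levels were not computed. The correction is worth making because the SAP states an error-control property that its calibration does not provide.

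**What to change.** Before unblinding, re-run the existing threshold simulation over a preset range of placebo declines and of other-dose effects: beneficial, inert and harmful. Then do one of two things:

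- set each cutoff so that its node holds its level over that range; or
- restate 6.5 and 6.11.2 as control under the all-null scenario only, and report the achieved node levels across the range.

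In the post-unblinding sensitivity analysis, keep the cutoffs fixed and report their achieved level over the preset range of declines. Do not re-derive them from the observed placebo mean.

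The cost is extra simulation and SAP wording, plus either a slightly stricter cutoff or a less favourable stated claim.

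Gating on Pr(DPR<1) would remove the dependence on placebo decline, because the boundary would then be the null value. That changes the primary decision rule and is an option for the sponsor, not a required correction.

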### **6.11.3. Additional Exploratory Analyses of the Primary Outcome**

#### **6.11.3.1. Mixed Model Repeated Measures (MMRM)**

The change from baseline score on the iADRS at each scheduled postbaseline visit (according to the Schedule of Activities) during the treatment period will be the dependent variable. The model for the fixed effects will include the following terms: baseline score, pooled site, treatment, visit, treatment-by-visit interaction, baseline-by-visit interaction, concomitant AChEI and/or memantine use at baseline (yes/no), and age at baseline. Visit will be considered a categorical variable. The null hypothesis is that the contrast between the LY3303560 group versus placebo at the Visit 28, Week 104 (4 weeks after the final dose of LY3303560) equals zero. An unstructured covariance matrix will be used to model the within-subject variance-covariance errors. If the unstructured covariance structure matrix results in a lack of convergence, the following tests will be used in sequence: heterogeneous Toeplitz covariance structure, heterogeneous autoregressive covariance structure, heterogeneous compound symmetry covariance structure, and compound symmetry covariance structure. The Kenward-Roger approximation will be used to estimate the denominator degrees of freedom.

The primary time point for treatment comparison will be at Week 104. The treatment group contrast in least-squares mean change from baseline score on the iADRS scale and its associated p-value and 95% CI will be calculated for treatment comparisons of LY3303560 versus placebo using the MMRM model specified above.

#### **6.11.3.2. Natural Cubic Spline**

In addition to the DPM and MMRM models described above, the iADRS will be modeled using natural cubic splines (NCS) (Chambers and Hastie 1992). The postbaseline score on the iADRS at each scheduled postbaseline visit (according to the Schedule of Activities) during the treatment period will be the dependent variable, and the mean for each treatment group over the entire double-blind duration of the study will be modeled. The NCS model provides a type of smoothing function to the data, can adequately estimate longitudinal trajectories under a variety of shapes (e.g., linear, quadratic, etc.) for each treatment group, and is thought to be a more

natural parameterization than modeling the mean change from baseline over time. The degrees of freedom of the model can be prespecified to establish the level of smoothing of the data. The number and location of the “knots” are utilized to parse out different time periods where the data may transition from one shape to another to provide an adequate fit. The primary time point for treatment comparison will be at Week 104. The variance-covariance structure assumptions of the NCS model are the same as the MMRM model and the covariates used in the model would remain unchanged. The model would be estimated by restricted maximum likelihood using SAS PROC MIXED or the `gls` function from the `nlme` package in the R.

### 6.11.3.3. Minimization (Dynamic Allocation) Assessment

Minimization (dynamic allocation): Because treatment assignment followed a minimization procedure rather than a randomization algorithm, a randomization test (i.e., permutation test) along with the MMRM analyses to confirm the asymptotic inference for the MMRM analysis will be conducted (Proschan et al. 2011). The main features of the randomization test would be: 1) the patients’ covariates, responses and enrollment order would be considered fixed, 2) the sharp null hypothesis would be assumed (i.e., the patients responses would be assumed exactly the same under LY3303560 or placebo), 3) the exact minimization algorithm and exact pooling site algorithm would be reproduced in order to generate a null distribution of the test statistic from the MMRM, and 4) the p-value from the generated null distribution would be obtained by comparing the observed data p-value to the percentiles of the generated distribution. Because of the sample size of the study, the exact null distribution will be impossible to enumerate, but a Monte Carlo approach will be used with a large number of realizations (approx 10,000) to simulate the null distribution.

### 6.11.3.4. Delta Adjustment Tipping Point Analysis

Sensitivity to departures from the missing-at-random (MAR) assumption will be investigated using a tipping point analysis (Carpenter and Kenward 2013). This method is a sensitivity analysis in multiple imputation under the missing-not-at-random (MNAR) assumption that searches for a tipping point that reverses the study conclusion. Departures from MAR in the LY3303560 treatment groups will be assessed assuming that patients who discontinue the study have, on average, efficacy outcomes after discontinuation that are worse by some amount  $\delta$  compared to other similar patients with observed data (ie, compared to a value which would have been assumed under an MAR model). A series of analyses will be performed with increasing values of  $\delta$  until the analysis conclusion of a statistically significant treatment effect no longer holds. The value of  $\delta$  that overturns the primary results will represent a tipping point. An interpretation of clinical plausibility of the assumption underlying the tipping point will be provided.

Mean changes from baseline in iADRS scores will be analyzed based on data observed while the patient remains on study as well as data imputed using multiple imputation (MI) methodology for time points at which no value is observed. Imputed values in the LY3303560 treatment groups will first be sampled from an MAR-based multiple imputation model and then  $\delta$ -adjusted as described below.

Missing-at-random-based imputations will be generated for iADRS scores at each time point, and then a value of  $\delta = \{\Delta\}$  will be added to all imputed values in the LY3303560 treatment groups prior to analyzing multiply imputed data. This approach assumes that the marginal mean of imputed patient measurements is worse by  $\delta$  at each time point after discontinuation compared to the marginal mean of patients with observed data at the same time point. Analyses will be conducted with values of  $\delta$  starting from 0 with increments of 0.10 until the null hypothesis can no longer be rejected.

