## 6.11. Efficacy Analyses

### 6.11.1. Primary Outcome and Methodology

The primary objective of this study is to test the hypothesis that IV infusion of LY3303560 will slow the cognitive and/or functional decline of AD as measured by the composite measure iADRS compared with placebo in patients with early symptomatic AD. This will be assessed using a Disease Progression Model (DPM).

The iADRS at each scheduled visit (according to the SoA) during the treatment period will be the dependent variable. The DPM is as follows:

$$Y_{ij} = \gamma_i + e^{\theta T_i} \sum_{v=0}^j \alpha_v + \mathbf{x}'_i \boldsymbol{\beta} + \varepsilon_{ij}, i = 1, 2, \dots, k; j = 1, 2, \dots, l$$

where  $Y_{ij}$  denotes the clinical outcome at visit  $j$  for participant  $i$  and clinical outcome score at baseline (prior to treatment) is  $Y_{i0}$ .  $\gamma_i$  ( $i=1, 2, \dots, k$ ) represents the random participant effects.  $T_i$  denotes the treatment arm for participant  $i$ .  $T_i$  takes a value of 1 if a participant is randomized to the low dose, a value of 2 for high dose, and a value of 0 for placebo.  $e^{\theta T}$  is the disease progression ratio (DPR) for treatment  $T$  and  $e^{\theta T} = 1$  for placebo.  $e^{\theta 1}$  and  $e^{\theta 2}$  represent the DPR of the low dose and the high dose, respectively. Furthermore,  $\alpha_v$  is the change in mean cognitive score for placebo from visit  $v-1$  to  $v$ .  $\varepsilon_{ij}$  is the error term. Additional covariates  $\mathbf{x}_i$  will include pooled site ID, age, and baseline AChEI/memantine use (yes/no).

The DPM model assumes the treatment effect of LY3303560 is proportional to placebo over the course of the study. This proportionality assumption is similar to the assumption made in proportional hazards modeling of time to event data. The DPM includes generally diffuse priors on all parameters. The precision value for the prior distribution of all parameters is set to a small value; therefore, the prior distributions on all parameters have very little impact on the posterior distributions. No information or knowledge of the effect of LY3303560 from previous studies will be incorporated into the prior distributions, and the inference will be based on Study LMDC only. Diffuse priors will be used.

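### As specified, the tipping-point analysis in SAP 6.11.3.4 does not find the delta that overturns the primary DPM result, and the gap is widest for 1400 mg

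*SAP*

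**What the plan says.** - **Primary model.** SAP 6.11.2: "The primary efficacy analysis for this trial is the Bayesian DPM". SAP 6.11.1 gives its outcome: "The iADRS at each scheduled visit (according to the SoA) during the treatment period will be the dependent variable".
- **Primary decision rule.** Each test asks whether Pr(DPR<0.75) exceeds X, "where the value of X is determined via simulation to control the test at the corresponding alpha level". Two values are fixed: "The cutoff for the primary analysis of LY5600 is 0.51", and "the cutoff for LY1400 is 0.99928". The hypothesis behind them is in SAP 6.11.1: "The null hypothesis is that the DPR between the LY3303560 group versus placebo equals 1".
- **Tipping point.** SAP 6.11.3.4 seeks the delta that reverses the study conclusion and says it "that overturns the primary results will represent a tipping point". The analysis it then describes is: "Mean changes from baseline in iADRS scores will be analyzed based on data observed while the patient remains on study", together with multiply imputed values. Delta starts at 0 and rises by 0.10 until a statistically significant effect is lost and the null hypothesis is no longer rejected.
- **Default level.** SAP 6.1 sets pairwise tests at two-sided 0.05 unless otherwise noted. SAP 6.11.3.4 notes nothing else.

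**The concern.** The stated aim and the stated procedure do not match. The aim concerns a posterior probability of at least 25% slowing under the DPM. The procedure concerns loss of significance for a mean change. SAP 6.11.3.4 mentions neither the DPM, the DPR nor the two cut-offs, and does not say what model is fitted to the imputed data.

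SAP 5.2 plans for 30% dropout and SAP 6.3.1 relies on missingness at random or ignorable missingness. SAP 6.11.3.4 is the only analysis that departs from that assumption. The completer and per-protocol analyses (6.11.3.7, 6.11.3.8) restrict the population and do not fill that role. If the reported delta belongs to another test, readers will judge the robustness of the primary claim by the wrong number. For 1400 mg they could be given a tipping point for a claim that has already failed.

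**Working it through.** **1. The SAP's own figure.** The only related figure is power above 95% (SAP 5.2), from a simulation whose visit covariance is not given, so it cannot be reproduced exactly. In a normal approximation, the standard error of the DPR that gives a 2.5% any-arm false positive rate under the 0.6 rule is about 0.128. For 5600 mg (DPR 0.50), power is Φ[(0.75 - 0.253×0.128 - 0.50)/0.128] = Φ(1.70) = 95.5%. For at least one arm it is 96.6% without the 3-month delay, and about 91% if the delay is crudely treated as a 12.5% loss of effect. That is the right order of size. The point does not depend on it.

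**2. A mean-change test is a different test.** Inputs from SAP 5.2: 360/3 = 120 per arm, SD 20.9, and a difference of 0.50 × 19.56 = 9.78 points.
- 120 per arm: SE = 20.9×√(2/120) = 2.698, power = Φ(9.78/2.698 - 1.96) = 95.2%.
- 84 completers per arm (0.7×120): SE = 3.225, power = Φ(9.78/3.225 - 1.96) = 85.8%.

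It draws its information from Week 104, whereas the DPM pools all visits through one ratio.

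**3. The decision rules compared.** Assume a normal posterior with SD s and a sampling SE σ that is equal in both arms. The DPM rule passes when the estimated DPR is below 0.75 - s·z(X), where z(0.51) = 0.025 and z(0.99928) = 3.187. Suppose 0.51 corresponds to one-sided 0.025, so that (0.25 + 0.025s)/σ = 1.96. A two-sided 0.05 test of DPR = 1 passes below 1 - 1.96σ. The one-sided level implied for 1400 mg is Φ[-(0.25 + 3.187s)/σ]. The documents do not give s, so a range is shown. The low value comes from one simulated trial in step 4 (estimate 0.652, probability 0.9621): (0.75 - 0.652)/1.776 = 0.055. The high value sets s = σ, which gives 0.25/1.935 = 0.129.

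| s | 5600 mg passes below | 1400 mg passes below | Two-sided 0.05 test passes below | Implied one-sided level, 1400 mg |
|---|---|---|---|---|
| 0.055 | 0.749 | 0.575 | 0.749 | about 5×10⁻⁴ |
| 0.129 | 0.747 | 0.338 | 0.747 | about 1.5×10⁻⁷ |

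For 5600 mg the thresholds coincide by construction, so the difference there comes from the model. For 1400 mg the primary rule is far stricter than 0.025 at either end of the range, but how much stricter cannot be fixed from the documents.

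**4. Illustration by simulation.** There were 25 trials with 120 per arm, 30% monotone dropout, 10 missing-at-random imputations, an assumed visit grid and an assumed random-slope covariance. Delta moved in 1-point steps in the worsening direction. Rule (a) was a pooled ANCOVA of Week 104 change at p<0.05. Rule (b) was a random-intercept DPM, fitted by maximum likelihood with a normal posterior, against 0.51 and 0.99928.
- 5600 mg: 24 trials were evaluable. The DPM tipped later in 19, earlier in 3 and at the same delta in 2. Differences ran from -2 to +7 points.
- 1400 mg: 5 trials met 0.99928 at delta 0. The DPM tipped at 1 to 13 points and the significance rule at 14 to 20, a gap of 7 to 15.
- 1400 mg: in 6 further trials the DPM rule had already failed at delta 0, yet the significance rule still gave a tipping point of 1 to 10. In the other 14, both failed at delta 0.

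**5. Direction of delta.** SAP 6.3.2 defines iADRS as (85 - ADAS-Cog13) + ADCS-iADL, so higher is better. SAP 6.11.3.4 adds a delta that rises from 0 to the active arms while describing the outcome as worse. With delta added, simulated results that were significant at the start had not tipped by 40 points.

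**The case against.** The strongest reply is that a DPM refit was meant. SAP 6.11.3.4 contains no p-value and no named rival model. The SAP also uses null-hypothesis and significance language for the DPM, and it is loose about change from baseline: SAP 5.2 states the DPM claim in mean changes, and 6.11.3.8 couples the DPM with change from baseline and a least-squares-means null. On the kindest reading, rejecting the null means passing the cut-offs of 6.11.2, and the section would then do what it claims.

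That reading is possible but not written. Where the SAP wants the DPM rerun it says so: 6.1.1 for COVID-19 censoring, 6.11.3.8 for the per-protocol set and 6.14 for subgroups. Even with a DPM refit, an analyst who tested DPR = 1 at the default level would stop at a different delta from one who used Pr(DPR<0.75) against 0.99928.

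Three parts of the reply stand:
- The two-sided 0.05 stop rule is inferred from the default in SAP 6.1; 6.11.3.4 does not state it.
- A reader might infer that the mean-change delta says nothing about the primary claim, or that no such analysis could. The documents do not support that. Endpoint, arms and imputations are shared, the simulated 5600 mg deltas lie within a few points of each other, and a correctly specified refit would answer the question.
- A mean-change result that is non-significant at delta 0 while the DPM passes would itself be informative.

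**Conclusion.** The point holds as a defect of specification. As written, SAP 6.11.3.4 leads to the delta at which a mean-change test loses significance, and labels it as the delta that overturns the primary result. For 5600 mg the expected discrepancy is a few iADRS points in either direction. For 1400 mg it is larger and flatters robustness.

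The sizes are illustrative. They rest on 25 simulated trials, an assumed visit grid and covariance, an ANCOVA that the SAP does not name for this purpose, and a likelihood stand-in for the Bayesian fit. The alpha that the multiplicity graph gives 1400 mg could not be read from the available text. A reader might also infer that the 0.99928 cut-off is itself wrong; nothing here shows that.

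The weight is low. The analysis is exploratory and cannot change the primary decision. It still deserves correction, because no other analysis in the SAP tests the primary claim against missingness not at random.

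**What to change.** 1. For each arm that meets its primary cut-off, fit the primary DPM to the delta-adjusted imputed datasets, pool the posterior draws across imputations, and report the delta at which Pr(DPR<0.75) falls to 0.51 (5600 mg) or 0.99928 (1400 mg). Where an arm misses its cut-off, say that there is no positive claim to tip.
2. Apply delta in the worsening direction: subtract it from imputed iADRS values in the active arms, and state the sign.
3. Search on a coarse grid, for example 1-point steps, then refine towards the planned 0.10 near the crossing.
4. Keep the mean-change version as a companion. Name its model and test level, and label its delta as belonging to that test. If it is the only version kept, delete the statement that its delta overturns the primary results.

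Cost: SAP wording and computing. With 20 imputations and 20 delta values, both chosen here as an example, that is 20 × 20 = 400 DPM fits, plus those for refinement. One fit per imputation and delta serves both arms. No new data are needed.
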